We propose a 4-week HIIT intervention in adolescents (ages 13 to 18, inclusive) with NAFLD. Up to 150 adolescents at-risk for NAFLD will be recruited to be able identify enough number of subjects with NAFLD (prevalence of NAFLD in our cohort was 40%; see data analysis section below). Our goal is to have 46 subjects with NAFLD to complete the study. Subjects will be randomized to either an exercise group or control group at a 5:1 ratio.

Because the objective of the study is to assess the effect of exercise in hepatic steatosis, we will use a multi-step approach to identify subjects with NAFLD and without disqualifiers (see

[figure not shown]

Figure 2. Study Design. FMD, Flow-Mediated Dilation; DXA, Dual X-Ray Absorptiometry; OGTT, Oral Glucose Tolerance Test; MRI, Magnetic Resonance Imaging; ACNC, Arkansas Children’s Nutrition Center; HIIT, High-Intensity Interval Training. *These assessments will only be completed if Visit 5 takes place at ACNC. Note: Physical Activity (PA) assessment via FitBit will also be conducted throughout the study.

exclusion criteria). When available, electronic medical records will be reviewed to identify potential participants. Eligibility will be assessed using a screening form. Potential participants may be screened over the phone or in person. If determined eligible, potential participants will be invited to attend a study visit. Study visits will take place at the Arkansas Children’s Nutrition Center (ACNC) and/or Arkansas Children’s Hospital. Parents and/or participants will be instructed not to come to the study visit and other assessments if parent and/or participant is ill. The visit/assessments will be rescheduled if that is case to a time when parents and participants are well and asymptomatic. **Figure 2** summarizes the study visit schedule for the exercise and control groups as described in detail below.

Participants will be asked not to eat or drink anything (except water) after 10 pm the night prior to the study visits. Due to fasting, study visits will be scheduled in the morning. Study compensation will be provided via ClinCard and/or gift card(s). Lunch and/or snacks may be offered to participants and/or parents at study visits.

Baseline/Pre-Intervention: All Subjects

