- **Randomization:** Participants will be randomized to the control or exercise group. We will employ a randomized block design with sex as the blocking factor. Participants who are randomized to the control group will not undergo any exercise training. If randomized to the exercise group, participants will be offered to tour the exercise facility for familiarization with location and personnel.

Participants will be compensated with \$25 at the end of the visit. A FitBit activity tracker will be provided for those who complete the study visit to account for differences in activity level at baseline and throughout the study.

Exercise Intervention (High-Intensity Interval Training (HIIT)): Exercise Group Only

HIIT Intervention – Exercise sessions will take place in the ACNC fitness facility. The session will begin with a 5-10 minute low-intensity warm-up, followed by ten 1-minute intervals using exercise equipment (such as elliptical machine and/or bike and/or treadmill) at a work rate that elicits 80-90% of the maximal heart rate determined during the VO_{2max} test. The participants will have two minutes to recover between each effort and will be encouraged to continue to turn the "pedals" over or walk slowly between high-intensity efforts. To finish the session, the participants will perform a 5-10 minute cool-down at a low intensity. Duration and/or intensity may be adjusted, if needed. Each participant will be asked to attend 3 weekly training sessions for 4 weeks. A minimum compliance rate of 50% will be required to remain in the study (at least 6 training sessions) by the end of the training period (4 weeks). Participants will be encouraged to do home exercises in between training sessions, but these will not be recorded other than via FitBit. All exercise sessions will be primarily directed and monitored by an exercise trainer who staffs the Core. However, an exercise physiologist may also conduct exercise training. The exercise trainer or exercise physiologist will monitor heart rate and OMNI score during sessions. Each HIIT exercise session is expected to last up to 1 hour. Compensation will be provided in increments of \$10, \$20, \$30 and \$40 at the end of the 3rd, 6th, 9th and 12th HIIT exercise sessions, respectively. Therefore, participants who attend all 12 HIIT sessions will receive a total of \$100.

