Participants can bring a friend or family member to workout with them if they would like. A separate release will be signed by the friend or family member in order to workout at the ACNC fitness facility.

5-Week/Post-Intervention: All Subjects

Study Visit 3 – This visit may last up to 3 hours and include: measurement of body mass and height, FMD, pregnancy screening (if female), DXA, and fitness test as described above. Participants who are in the control group will complete this visit 5 weeks \pm 1.5 week after study visit 2. Participants will be reimbursed for their time with \$25 at the end of the visit.

Study Visit 4 – This visit may last up to 4 hours and include: measurement of body mass and height, vital signs, OGTT, FibroScan, urine collection, and dietary questionnaire as described above. Participants will be reimbursed for their time with \$50 at the end of the visit.

3-Month Follow-up: Exercise Group Only

Study Visit 5 – Participants from the exercise group will be asked to attend a follow-up visit 3 months \pm 2 week after last HIIT session. This visit may last up to 4 hours and include: measurement of body mass and height, hip and waist circumference, vital signs, pregnancy screening (if female), DXA, FibroScan, FMD, OGTT, urine collection, and dietary questionnaire as described above. FMD, pregnancy screening (if female) and DXA will only be completed in the instance that this visit takes place at ACNC. Participants will be reimbursed for their time with \$50 at the end of the visit.

Magnetic Resonance Imaging (MRI)

In addition to the study procedures described above, all participants will complete a MRI scan before the baseline/pre-intervention fitness test, and another MRI scan before the 5-week/post-intervention OGTT. Furthermore, participants in the exercise group will complete an additional MRI scan before the 3-month follow-up OGTT. The MRI scans will be done at the Arkansas Children's Hospital Radiology Department for the determination of hepatic fat content via magnetic resonance imaging. Each visit for completion of a MRI scan will last up to 1.5 hours. Participants will be reimbursed for their time with \$50 after each visit.

Physical Activity Assessment

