Samples will be stored in freezers in the Arkansas Children's Nutrition Center and/or Arkansas Children's Research Institute. The freezers are constantly monitored to ensure that the proper temperature is maintained. Samples will be identified using the subject's unique study acronym along with the date of sample collection and type of sample (e.g. EDTA plasma, serum). Remaining samples may be stored indefinitely or until used up for future analyses. If consented, samples may be used in future studies related liver and/or metabolic health. Participants and/or parents may contact the study's principal investigator, if they choose to withdraw consent to use samples and/or information in future research. In this case, a written letter addressed to the principal investigator expressing their desire to withdraw their consent would be required. If the information and/or samples have been shared or if publication of results has occurred, then we may not be able to remove information and/or samples.

Data Analysis

Exploratory data analysis will be conducted prior to formal statistical analysis. We will examine the distributions of all key variables to check for data errors and ensure that modeling assumptions are not violated. Numerical summaries including means, standard deviations, medians and histogram graphical techniques will be used for continuous variables and frequencies will be computed for categorical variables. For both aims, the primary outcome is IHTG level measured by both FibroScan and MRI, and secondary outcomes are fitness level, and various cardiometabolic disease markers (i.e.; insulin, glucose, adiponectin, etc.). The immediate (Aim 1) and sustained (Aim 2) effect of HIIT will be measured by comparing the changes in outcomes between groups using a linear mixed-effect framework with a subject-level random intercept. Changes in the outcomes are defined as difference between follow up visits (5-week and 3-month) versus the baseline. The independent variables will be group (intervention vs control), visit time (baseline, 5-week, 3-month) and their interaction term. This model specification can test the effect of intervention as well as difference between visits, while correctly account for the within-subject correlation due to repeated visits. Post-hoc contrasts of visit time between 5-week and baseline will be used to test the hypotheses under Aim 1, while contrasts between 3-month and 5-week will be used to test the hypotheses under Aim 2.

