As an exploratory aim, diagnostic performance of FibroScan for the NAFLD adolescent will be determined by discriminating NAFLD status defined by FibroScan against that by MRI to calculate sensitivity, specificity, positive and negative predictive values. Additional agreement statistics such as concordance correlation coefficient and Bland-Altman plots will be provided for the continuous measurements of IHTG levels measured by both methods.

In our pilot data, the IHTG levels were 11.5 ± 5.4 percent at baseline for NAFLD subjects (N=23). With a pre-defined clinically significant change of 20% relative decrease from baseline, we expect the NAFLD subjects' fat percent will be decreased to an average of 9.2 ± 5.4 percent after HIIT intervention, which is an equivalent effect size of 0.43. In order to detect this effect size at 80% power, we will need 38 NAFLD participants in the intervention group, therefore 8 NAFLD subjects in the control group. Accounting for a 20% dropout rate and false-negative screening from FibroScan, we propose to enroll 58 subjects with NAFLD. Therefore, we need to screen no less than 150 subjects at-risk for NAFLD at baseline, to be able to identify 58 subjects with NAFLD (NAFLD prevalence was 40% in our pilot study, see preliminary data section above).

Ethical Considerations

This study will be conducted in accordance with all applicable government regulations and the University of Arkansas for Medical Sciences research policies and procedures. This protocol and any amendments will be submitted and approved by the UAMS Institutional Review Board (IRB) to conduct the study.

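### Exercise-arm participants must attend 6 of 12 sessions after randomisation to stay in the study, and no analysis set as randomised is named

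*Combined protocol and SAP*

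**What the plan says.** Participants are randomised 5:1 at Study Visit 2, before any training. The exercise arm is then asked to train three times a week for four weeks. The section on the HIIT intervention, which applies to the exercise group only, adds: "A minimum compliance rate of 50% will be required to remain in the study (at least 6 training sessions". Compliance is judged at the end of the four weeks. Controls do no training and have no equivalent condition.

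The next section is headed "5-Week/Post-Intervention: All Subjects". For Visit 3 it says "Participants who are in the control group will complete this visit 5 weeks" (with a window) after Visit 2. The MRI section says "all participants will complete a MRI scan before the baseline/pre-intervention fitness test, and another MRI scan before the 5-week/post-intervention OGTT". Neither section says what happens to someone with fewer than six sessions. The 3-month visit is for one arm: "Participants from the exercise group will be asked to attend a follow-up visit 3 months" after the last HIIT session, again with a window.

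The Data Analysis section specifies a linear mixed model with a subject-level random intercept: "The independent variables will be group (intervention vs control), visit time (baseline, 5-week, 3-month) and their interaction term". It names no analysis set, as randomised or otherwise, and does not say how missing outcomes are handled. The sample size counts completers. Study Design and Procedures says "Our goal is to have 46 subjects with NAFLD to complete the study", and Data Analysis says "In order to detect this effect size at 80% power, we will need 38 NAFLD participants in the intervention group", with 8 controls.

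**The concern.** The rule selects participants in one arm on what they did after randomisation, before the primary outcome is measured. Adolescents who attend at least half their sessions may differ from those who do not in motivation, health, diet or family support, and these may also affect liver fat. Controls are not filtered in this way, so randomisation no longer guarantees that the groups compared are alike apart from HIIT.

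Low attendance is a realistic prospect. The background section says that most adolescents struggle to adhere to lifestyle changes, and compensation rises in steps with sessions attended.

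Objective/Specific Aims gives two uses for the results: guiding providers in using HIIT as treatment, and supplying preliminary data for mechanistic work. A subset with a minimum amount of training can serve the second. The first also needs the result in everyone assigned to HIIT.

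For Aim 2 the 3-month data come from the exercise arm alone, so selection there mainly narrows whom the result describes.

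**Working it through.** **The plan's own figures.** Three sessions a week for 4 weeks is 12, and 6/12 = 50%. Completers are 38 + 8 = 46, and 46/(1 − 0.20) = 57.5, rounded up to the stated 58. At 5:1, 58 × 5/6 = 48.3, so about 48 in the exercise arm; a 20% loss leaves about 38. Enrolment therefore makes up the numbers lost, but it does not undo selection. The 20% covers dropout and false-negative FibroScan screening together and is not a forecast of low attendance.

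**Shift in the contrast if HIIT has no effect.** Assumptions: a fraction *q* of the exercise arm, those lowest on a normally distributed attendance propensity, is removed. That propensity has correlation *r* with the improvement that would have occurred anyway. The documents give neither *q* nor *r*, and the sign of *r* is unknown.

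- Standard error of the difference in mean change, in units of the SD of change: √(1/38 + 1/8) = 0.389.
- Shift in the retained mean, in the same units: *r* × φ(z_q)/(1 − *q*).
- *q* = 0.20: 0.035, 0.070 and 0.105 at *r* = 0.1, 0.2 and 0.3. Divided by 0.389, these are 0.09, 0.18 and 0.27 standard errors, whatever the SD.
- *q* = 5/48 (about half the loss due to low attendance, the rest random): 0.05 standard errors at *r* = 0.1 and 0.16 at *r* = 0.3.

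**Type I error.** Simulated with no true effect: 48 exercise participants, the lowest 10 on attendance removed, 38 against 8, pooled t-test on change, 1,000,000 runs.

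| r | Two-sided error | Favouring HIIT, r positive | Favouring HIIT, r negative |
|---|---|---|---|
| 0 | 5.0% | 2.5% | 2.5% |
| 0.1 | 5.1% | 3.1% | 2.0% |
| 0.2 | 5.5% | 3.8% | 1.7% |
| 0.3 | 6.2% | 4.8% | 1.4% |

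With 5 removed for low attendance and 5 lost at random, two-sided error is 5.1% at *r* = 0.1 and 5.5% at *r* = 0.3.

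**Effect in everyone assigned to HIIT.** The plan expects a fall from 11.5 to 9.2, which is 2.3 points. Suppose 2.3 is the fall in those who attend enough, and low attenders gain nothing. The mean fall over all assigned is then 2.3 × 0.9 = 2.07 with 10% low attenders, or 2.3 × 0.8 = 1.84 with 20%. An analysis of retained participants would still report 2.3, an excess of 0.23 or 0.46 points. If low attenders gain half as much (1.15), the excess is half that.

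**Cost in numbers, on the same assumptions.** Keeping power against the diluted effect needs (1/0.9)² = 1.23 or (1/0.8)² = 1.56 times the analysed participants. Low attenders now count towards the analysis, so recruitment rises less:

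- Exercise arm, 10%: 38 × 1.235 = 46.9 against 38/0.9 = 42.2, a ratio of 1.11.
- Exercise arm, 20%: 38 × 1.5625 = 59.4 against 38/0.8 = 47.5, a ratio of 1.25.
- Both arms: (46.9 + 9.9)/(42.2 + 8) = 1.13 and (59.4 + 12.5)/(47.5 + 8) = 1.30.

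**The case against.** **The sections can be read together.** Someone who has not remained in the study is no longer a subject, so the heading and MRI wording need not contradict the attendance rule. That reading is possible, but it confirms that low attenders go unmeasured. The other reading, that everyone randomised is measured, conflicts with the rule. The text has to say which is meant.

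**A mixed model can use incomplete records.** It can, and it is valid if data are missing at random. But a removed participant supplies only a baseline value, which says almost nothing about change. Removal is driven by attendance, which the model does not contain, so the assumption is doubtful. Adding attendance as a covariate is not the answer, because controls have none and it arises after randomisation. The remedy is to measure the outcome.

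**The numbers are small and assumed.** This stands. The removed share and *r* are assumptions, and half the sessions is a lenient threshold. The simulation uses a t-test on change rather than the planned model. It removes 10 of 48 (20.8%), while the shift was computed at 20%. At *r* = 0.3 the error is still 5.3% with the mean shift taken out, so about a quarter of the excess, (5.3 − 5.0)/(6.2 − 5.0), comes from reduced variance in the exercise arm.

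**The dilution figures assume that 2.3 points applies to attenders.** Data Analysis does not say so. If 2.3 is already the average over all assigned, the multipliers do not apply and the change costs less.

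**The aims are largely mechanistic.** A minimum exposure is defensible for that purpose, and the fix keeps it. But excluding low attenders from one arm does not isolate efficacy either, because selected attenders are compared with unselected controls.

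**Conclusion.** The concern holds. Followed as written, the rule alters the randomised comparison for the primary outcome through behaviour after randomisation in one arm, and nothing elsewhere in the document retains low attenders or names an analysis as randomised. The rule on keeping data already collected, under Ethical Considerations, covers only withdrawal of consent and stops further collection.

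In the illustration the effect on testing is close to nominal at small correlations and modest at 0.3. The plan gives no low-attendance rate, and the sign of the bias is unknown. The case therefore rests mainly on the loss of the randomised comparison and on outcomes that no later analysis can recover. This should be changed while follow-up can still be collected; the figures do not show that it would invalidate the trial.

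**What to change.** - Amend the HIIT section so that low attendance does not end follow-up, and align the 5-week and MRI sections with it.
- Invite all randomised participants to Visits 3 and 4 and the 5-week MRI, and all exercise-arm participants to Visit 5 and the 3-month MRI, whatever their attendance.
- Give Visit 5 an anchor date that does not depend on the last session attended, for example the scheduled end of training. For participants who train to that date the interval is unchanged.
- In Data Analysis, define the primary analysis as all randomised participants in their assigned group, using all available data in the planned mixed model, and state how missing 5-week values are handled.
- Keep six or more sessions as the definition of a secondary analysis of adherent participants.

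The cost is a short amendment, visits and scans for low attenders, and a diluted average effect. The training schedule does not change. No added enrolment is proposed, but the dilution should be acknowledged where power is stated.

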Non-Alcoholic Fatty Liver Disease (NAFLD) is characterized by fatty infiltration (steatosis \geq 5% of liver volume) and is the most common chronic liver disease of childhood. The estimated prevalence of NAFLD is 29% to 38% in obese children¹. NAFLD is rare before puberty, but can be diagnosed during puberty. Routine screening for NAFLD is recommended in at-risk groups and is done via measurement of serum alanine aminotransferase (ALT) level, but this test has a low specificity¹. Using Magnetic Resonance Imaging (MRI), a reference diagnostic test, we demonstrated that 40% of obese children (10-17 years) who attended to our weight management clinic had NAFLD. Twice the sex-specific ALT level, a recommended cut-point for further evaluation¹, had only 30% specificity in our cohort. Further, ALT levels do not correlate with the stage of steatosis or fibrosis.² Recent findings suggest that the degree of hepatic fat content (i.e., Intrahepatic triglyceride [IHTG] percent) in patients with NAFLD plays an independent role in progression of disease to advanced characterized by inflammation (Non-Alcoholic Steatohepatitis [NASH]) and fibrosis^{3,4}. This notion is supported by the finding that among adult NAFLD patients with no baseline fibrosis, those with a higher baseline IHTG (\geq 15.7%) developed fibrosis at a much higher rate (OR 6.67, 95% CI:1.01-44.1, $p < 0.05$) after a 1.75 year follow up⁵.

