Based on available literature and our pilot data (shown below), **we hypothesize that insulin resistance (IR) and decreased cardiac fitness are central to the NAFLD in adolescents, and the degree of steatosis is negatively correlated with lower fitness and higher IR. Thus, exercise-driven improvements in IHTG levels will be positively associated with the increase in fitness and the decrease in IR levels in adolescents with NAFLD.** We will test our hypotheses through the following specific aims:

Aim 1: Assess the change in IHTG, and CVD and IR markers in subjects with NAFLD after 4 weeks of HIIT, compared to a sex-matched control group also with NAFLD with no training.

1A. Quantitate the change in IHTG. Hypothesis: IHTG will decrease after HIIT, and the change will be greater than that seen in controls.

1B. Measure the changes in fitness and markers of CVD. Hypothesis: HIIT will significantly increase fitness, decrease heart rate variability and blood pressure, and improve atherogenic lipid profile. The changes will be greater than that seen in controls. Changes in fitness and IHTG will correlate.

1C. Estimate changes on IR. Hypothesis: HIIT will decrease IR especially in those with higher baseline IR, and the changes will be greater than that seen in controls. Changes in IR will correlate with changes in fitness and IHTG.

Aim 2: Determine the post-intervention effects of HIIT on IHTG, and CVD and IR markers 3 months after completion of the HIIT in adolescents with baseline NAFLD.

2A. Quantitate the change in IHTG percent. Hypothesis: HIIT will have a sustained positive effect on IHTG, and that IHTG 3-months post-HIIT will be significantly lower compared to baseline level.

2B. Estimate changes on IR and other CVD markers. Hypothesis: HIIT will have a sustained positive effect on IR, and that IR 3-months post-HIIT will be significantly lower compared to baseline level.

Pediatric NAFLD has serious cardio-metabolic health outcomes. Findings of this study will inform clinical providers in the use of HIIT as a modality to treat adolescent NAFLD and associated morbidities, and produce preliminary data for mechanistic studies to probe pathways implicated in the pathogenesis of NAFLD.

Preliminary Results

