We have successfully recruited 59 obese children for a pilot study and characterized their metabolic profile, including IHTG (via MRI)⁵⁹. Forty percent of children had NAFLD in this cohort. Children with NAFLD have decreased cardiorespiratory fitness: We assessed fitness using continuous treadmill graded protocol⁶⁰. While most healthy individuals are expected to walk 9-12 minutes, the duration was only 4.5 ± 3 min (range 1-7 min) in our cohort (either due to exertion or target heart rate been achieved). Elevated blood pressure (BP) was more prevalent in NAFLD group: Sixty percent of children with NAFLD had elevated BP z-score (adjusted for age, height, sex) compared to 33% of children without NAFLD. Children with NAFLD have higher IR: While all subjects had elevated IR as assessed by HOMA-IR, children with NAFLD had even higher HOMA-IR levels. Also, adiponectin (as an indirect marker for IR) was lower , and FGF21 was higher (likely a compensatory response) in NAFLD group (**Table 1**). IR and elevated FGF21 have an additive effect on IHTG: When all children were stratified based on their median HOMA-IR and FGF21 levels, those with $HOMA-IR \geq 5.67$ and $FGF21 \geq 145.2$ pg/mL had higher IHTG percent compared to other groups (**Figure 1**). Association of FGF21 and IHTG was dependent on the magnitude of IR. HOMA-IR values of the last two groups were comparable (9.74 ± 3.65 vs. 9.18 ± 4.56 , $p=0.71$). Taken together, our results and published literature^{11,61-63} suggest that IHTG relates to insulin, FGF21, and adiponectin actions collectively. Strategies aiming to decrease IR and improve FGF21 sensitivity while increasing adiponectin levels could reduce IHTG and treat NAFLD.

NAFLD Status	NAFLD (+) (n=24)	NAFLD (-) (n=35)	P value
IHTG %	11 ± 5.4	2.8 ± 1.1	<0.001
BMI (kg/m ²)	39 ± 6.8	36 ± 5.3	0.04
Body Fat (%)	45.5 ± 6.1	43.3 ± 6.3	0.2
HOMA-IR	8.1 ± 4.1	5.7 ± 4	0.02
ALT (IU/L)	38.3 ± 14.3	29.2 ± 12.2	0.01
Adiponectin (ng/mL)	6.6 ± 3.3	8.3 ± 3.7	0.07
FGF21 (pg/mL)	185 ± 123	140 ± 84	0.10

[figure not shown]

Figure 1: IHTG per median HOMA-IR and FGF21 in obese adolescents (n=58).

Study Design and Procedures

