- Anthropometrics & Vital Signs: Body mass and height will be obtained using standardized techniques. In addition, we will also measure waist and hip circumferences using a tape measure. Blood pressure and heart rate will be assessed using standard techniques. If necessary, participants may be provided with a gown. Measures will be taken in duplicate, or triplicate if not within acceptable agreement.
- FibroScan: A FibroScan (FibroScan® 530 Compact, Echosens, Paris, France) will be performed to determine NAFLD status based on Controlled Attenuated Parameter (CAP) score. FibroScan, similar to an ultrasound scan, is a technique to assess liver health. FibroScan is a routinely used clinical tool in most centers to assess liver health. Outcomes of FibroScan are “Controlled Attenuated Parameter (CAP)” and “Transient Elastogram (TE)”. CAP measurement strongly correlates with steatosis, while TE measures the stiffness of the liver as a surrogate marker of fibrosis, as described above. CAP values range from 100 to 400 dB/m, and higher numbers indicate more pronounced steatosis. TE values range from 2.5 kPa to 75 kPa, and higher numbers indicate more pronounced stiffness (fibrosis). Measurement via FibroScan is done when the subject is lying down on his/her back. The test involves a probe being passed over the right upper quadrant of the abdomen to measure the liver fat content and stiffness. The results are then immediately available for review once the scan is complete. No special preparation is required before the FibroScan. We will use the CAP cut-point of 241 dB/m as suggested by Shin et al. to determine baseline steatosis.⁶⁶ A subject with a CAP score of 241 dB/m or greater will be accepted as having steatosis. FibroScan test takes about 20 minutes to complete including the generation and interpretation of the results.

In the rare instance that a valid scan is not feasible, the participant will be accepted as having NAFLD and will be allowed to proceed with the study. If upon initial Magnetic Resonance Imaging (MRI), the participant is found not to have NAFLD, then participation will be discontinued at that time.

Out of the participants whose eligibility is confirmed:

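### The primary outcome names two instruments on different scales, with no ranking or success rule; the agreement and baseline accuracy analyses have related problems

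*Combined protocol and SAP*

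**What the plan says.** **Primary outcome.** Data Analysis defines it once, for Aims 1 and 2 together: "the primary outcome is IHTG level measured by both FibroScan and MRI".

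**What FibroScan measures.** Under Study Visit 1, FibroScan yields CAP, for steatosis, and a stiffness value in kPa. On the first, "CAP values range from 100 to 400 dB/m, and higher numbers indicate more pronounced steatosis". No section converts CAP to fat percent.

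**Pointers to MRI percent.** The opening background section describes its earlier cohort work as "Using Magnetic Resonance Imaging (MRI), a reference diagnostic test". Preliminary Results says the pilot "characterized their metabolic profile, including IHTG (via MRI", with the table in percent. Aim 2A is to "Quantitate the change in IHTG percent". The sample size paragraph works only in fat percent.

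**Entry.** "A subject with a CAP score of 241 dB/m or greater will be accepted as having steatosis". If no valid scan can be obtained, NAFLD is presumed and MRI then decides: "If upon initial Magnetic Resonance Imaging (MRI), the participant is found not to have NAFLD, then participation will be discontinued at that time". The criteria for continuing in the study accept NAFLD shown by CAP or by MRI and refer back to this text.

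**Exploratory aim.** Data Analysis compares NAFLD status by FibroScan with status by MRI (sensitivity, specificity, both predictive values). It adds a concordance correlation coefficient (CCC) and Bland-Altman plots for the continuous values.

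**The concern.** A variable in dB/m and a variable in percent are two outcomes, even if both reflect liver fat. Aim 1A predicts that "IHTG will decrease after HIIT, and the change will be greater than that seen in controls". If MRI supported this and CAP did not, or the reverse, the plan could not say whether the hypothesis was met, and the choice could be made after the results were seen.

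The exploratory analysis has two further problems. CCC and Bland-Altman need both methods on one scale. Sensitivity, specificity and NPV need participants who are negative on FibroScan and also have an MRI, and the entry rule appears to remove them at baseline.

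**Working it through.** **1. The plan's own figures.** From the sample size paragraph in Data Analysis:
- Effect size: (11.5 − 9.2)/5.4 = 0.426, stated as 0.43.
- Intervention group: a within-group t-test at 80% power needs 35–36 participants with one-sided alpha 0.05, and 45–46 with two-sided 0.05. The stated 38 lies near the one-sided figure.
- Controls: 38/5 = 7.6, so 8.
- Enrolment: 46/(1 − 0.20) = 57.5, so 58.

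Every input is in fat percent. The documents give no CAP standard deviation and no expected CAP change, so power for CAP cannot be computed.

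**2. False-claim rate if either variable counted.** This is a scenario, not a rule in the plan. Under no effect, take the two test statistics as bivariate normal with correlation ρ (assumed) and a directional claim, as in Aim 1A. With per-test error a and critical value c:

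P(either) = 2a − P(Z₁ > c and Z₂ > c)

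| ρ | a = 2.5% (two-sided 0.05) | a = 5% (one-sided 0.05) |
|---|---|---|
| 0 | 4.94% | 9.75% |
| 0.5 | 4.54% | 8.78% |
| 0.7 | 4.17% | 8.04% |
| 0.9 | 3.52% | 6.81% |

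For example, at ρ = 0 and a = 5%: 2 × 0.05 − 0.05² = 0.0975. Both columns are shown because the documents state neither alpha nor sidedness.

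**3. CCC across units.** CCC = 2·r·s₁·s₂/(s₁² + s₂² + D²), where D is the difference in means.
- MRI: 11.5 ± 5.4 (sample size paragraph).
- CAP mean: 241, the entry cut-off. A higher mean makes D larger.
- CAP SD: 30 to 60 dB/m (assumed).
- r = 1, and D = 241 − 11.5 = 229.5.

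SD 30: 2 × 5.4 × 30/(29.16 + 900 + 52,670.25) = 324/53,599.4 = 0.006.

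SD 60: 2 × 5.4 × 60/(29.16 + 3,600 + 52,670.25) = 648/56,299.4 = 0.012.

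Perfect correlation would thus give a CCC of about 0.01. The Bland-Altman bias would be 229.5 in no definable unit.

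**4. Baseline 2×2 table at 241 dB/m.** On the natural reading, participants reach the baseline MRI with CAP of 241 or more, or with no valid scan. Those without a valid scan cannot be classified by CAP. The CAP-negative row is then empty or nearly so: true negatives ≈ 0 and false negatives ≈ 0. If it is exactly empty, sensitivity = TP/(TP + 0) = 100%, specificity = 0/(0 + FP) = 0% whenever FP > 0, and NPV = 0/0. PPV = TP/(TP + FP) can still be estimated. The enrolment figure allows for false-negative FibroScan screening, which such a table could not show.

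**The case against.** The strongest reply is that MRI percent is plainly the intended primary outcome: it is the reference test, the pilot measure, the scale of Aim 2A and the scale of the sample size. That stands as evidence of intent and narrows the practical ambiguity. It does not settle the matter, because the one sentence that defines the primary outcome names both instruments. The rule that lets MRI decide concerns eligibility after a failed scan, not conflicting outcome results.

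A reader might infer that the plan allows success to be claimed on either measure, or requires both. It says neither, so the error rates above show what is left open and are not properties of a stated rule. Power figures for a both-required rule would describe no test in this plan, since no CAP power can be derived.

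A reader might also infer that sensitivity of 100% and specificity of 0% are guaranteed. The documents stop short of that:
- The continuation criterion says CAP or MRI, and its back-reference to the failed-scan case is natural but not explicit.
- Recruitment may draw on an earlier study whose participants had NAFLD on MRI.
- No sentence expressly ends participation for CAP below 241, as there is for exercise safety, puberty and diabetes. The exclusion for recent evidence of no NAFLD, which includes FibroScan, favours the natural reading.
- The accuracy analysis is not confined to baseline, and CAP could fall below 241 at later visits.

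Finally, the agreement and accuracy analyses are labelled exploratory and decide neither aim. That limits their weight but does not make a comparison of dB/m with percent meaningful.

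**Conclusion.** The point holds. As written, the plan has two primary variables in different units, with no ranking, success rule or alpha sharing, and its sample size supports only fat percent. This rests on the text and needs no assumption.

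The size depends on assumptions. If either result counted, the false-claim rate would be 3.5–4.9% against 2.5% per test, or 6.8–9.75% against 5%, for ρ from 0.9 to 0.

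The CCC and Bland-Altman analysis is wrong as written. The CCC of about 0.01 at perfect correlation depends on the assumed CAP SD and mean, but the mismatch of units does not. Baseline sensitivity, specificity and NPV at 241 dB/m would be uninformative on the natural reading of the entry rule, which is likely but not certain.

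The trial is not invalidated, because the intent can be inferred. The text should be corrected before results are seen.

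**What to change.** - In Data Analysis, state: *The primary outcome for both aims is IHTG percent by MRI; FibroScan CAP (dB/m) is a secondary outcome reported in its own units.* A hierarchical, co-primary or alpha-sharing rule would also remove the ambiguity, but MRI percent is the choice that the existing sample size supports.
- Replace the raw CCC and Bland-Altman plots with a correlation and a regression of MRI percent on CAP that accounts for repeated visits. Keep the agreement statistics only if a CAP-to-percent conversion is specified in advance.
- At baseline and 241 dB/m, report PPV only, and explain that the entry rule prevents useful estimates of sensitivity, specificity and NPV.
- Label any accuracy estimate from later visits as coming from a selected, mostly trained sample.

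The cost is wording and a small change to the analysis code; sample size and visits are unchanged. CAP can no longer support a primary claim, and baseline sensitivity, specificity and NPV are given up.
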